7.2. Adverse Events list for psilocybin

Based on the studies presented in the previous section, the following adverse events might be expected after subjects are given the study agent.

7.2.1. Psychological adverse events

- Anxiety
- Negative emotional states
- Paranoid/delusional thinking

7.2.2. Physical adverse events

- Increased blood pressure
- Increased heart rate
- Nausea
- Headaches
- Fatigue
- Insomnia

Same participant.
 Same participant.

7.3. Adverse Event Characteristics

• CTCAE term (AE description) and grade: The descriptions and grading scales found in the revised NCI Common Terminology Criteria for Adverse Events (CTCAE) version 5.0 will be utilized for AE reporting. All appropriate treatment areas should have access to a copy of the CTCAE version 5.0. A copy of the CTCAE version 5.0 can be downloaded from the CTEP web site

http://ctep.cancer.gov/protocolDevelopment/electronic_applications/ctc.htm.

• For expedited reporting purposes only:

- AEs for the study agent that are listed above should be reported only if the adverse event varies in nature, intensity or frequency from the expected toxicity information which is provided.
- Other AEs for the protocol that do not require expedited reporting are outlined in the next section (Expedited Adverse Event Reporting) under the sub-heading of Protocol-Specific Expedited Adverse Event Reporting Exclusions.

• **Attribution** of the AE:

- Definite The AE *is clearly related* to the study treatment.
- Probable The AE *is likely related* to the study treatment.
- Possible The AE *may be related* to the study treatment.
- Unlikely The AE *is doubtfully related* to the study treatment.
- Unrelated The AE *is clearly NOT related* to the study treatment.

7.4. Adverse Event Reporting

- 7.4.1. In the event of an unanticipated problem or life-threatening complications treating investigators must immediately notify the Principal Investigator.
- 7.4.2. Investigators **must** report to the Principal Investigator any adverse event (AE) that occurs after initial dose, during treatment, or within 30 days of last treatment on the local institutional SAE form (eCRF).

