3.2 Exclusion Criteria

- 3.2.1 Current General Inpatient (GIP) hospice status
- 3.2.2 Patients currently receiving chemotherapy
- 3.2.3 Condition impairing oral intake or digestive absorption
- 3.2.4 Presence of a delirium diagnosed by the CAM (see Appendix A)
- 3.2.5 Significant suicide risk as defined by suicidal ideation with intend and a plan as endorsed on item 5 on the C-SSRS within the past month or at V0 (see Appendix A)
- 3.2.6 Current or past history of schizophrenia, psychotic disorder, bipolar disorder, delusional disorder, paranoid personality disorder, schizoaffective disorder, or borderline personality disorder, as assessed by medical history
- 3.2.7 History of allergic reactions attributed to compounds of similar chemical or biologic composition to psilocybin
- 3.2.8 Other personal circumstances and behavior that would limit compliance with study requirements, or judged by the study psychiatrist and/or principal investigator to be incompatible with establishment of rapport or safe exposure to psilocybin
- 3.2.9 Potential for adverse drug-drug interactions. Concomitant medications with significant potential to interact with study medications will be exclusionary if they cannot be tapered. These include the following:
 - Serotoninergic antidepressants
 - Centrally-acting serotonergic agents (e.g. MAO inhibitors)
 - Antipsychotics (e.g. first and second generation)
 - Mood stabilizers (e.g. lithium, valproic acid)
 - Aldehyde dehydrogenase inhibitors (e.g. disulfiram)
 - Significant inhibitors of UGT 1A0 or UGT 1A10

Any psychiatric medication will be tapered if possible in an appropriate fashion to avoid withdrawal effects. They will be discontinued long enough before the psilocybin Session to avoid the possibility of any drug-drug interaction (the interval will be at least five times the particular drug and active metabolites' half-life). See section 9 of the protocol for concomitant medications and tapering instructions.

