4 REGISTRATION PROCEDURES

4.1 General Guidelines for DF/HCC Institutions

Institutions will register eligible participants in the Clinical Trials Management System (CTMS) OnCore. Registrations must occur prior to the initiation of any protocol-specific therapy or intervention. Any participant not registered to the protocol before protocol-specific therapy or intervention begins will be considered ineligible and registration will be denied.

An investigator will confirm eligibility criteria and a member of the study team will complete the protocol-specific eligibility checklist.

Following registration, participants may begin protocol-specific therapy and/or intervention. Issues that would cause treatment delays should be discussed with the Principal Investigator (PI) of the registering site. If the subject does not receive protocol therapy following registration, the

subject must be taken off study in the CTMS (OnCore) with an appropriate date and reason entered.

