4.3 General Guidelines for Other Investigative Sites

Eligible participants will be entered on study centrally at Dana-Farber Cancer Institute by the Study Coordinator. All sites should email the Sponsor ([contact]) to confirm and plan intervention. The required forms can be found in Appendices. Following registration, participants should begin intervention within 7 days. Issues that would cause intervention delays should be discussed with the Principal Investigator. If the subject does not receive protocol therapy following registration, the subject must be taken off study in the CTMS (OnCore) with an appropriate date and reason entered.

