Patients who signed the inform consent form (ICF) or the electronic ICF (eICF) will have a first visit (V0) with the study psychiatrist and the investigator, taking place either at their home or remotely, to confirm their eligibility, and complete screening assessments including: the Demoralization Scale-II (DS-II); the Columbia-Suicide Severity Rating Scale (C-SSRS); the Confusion Assessment Method (CAM) and medical and psychiatric history. Physical examination and vital signs will be obtained from the clinical team and/or patient chart and reviewed by the study psychiatrist and the investigator. The lead physician will review last available bloodwork and exclude patients who have elevated AST and ALT five times above the normal laboratory limit. The lead physician as part of the medical evaluation will observe for clinical signs of liver disease, including confusion, asterixis or jaundice. Patients with these symptoms suggestive of liver failure will be excluded from the study. Only patients who meet all eligibility criteria will be enrolled in the study. Caregivers of enrolled patients will be offered to consent for the caregiver survey (CarGOQoL), the HADS, and the post-intervention qualitative interview. The study staff will follow the registering processes described in Section 4.0.

The duration of V0 will be 30-60 min.

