5.1.2 Treatment regimen

Version Date: April 18, 2023

Visit V1: baseline assessment + preparation session #1 (patient's home or remote)

V1 includes baseline assessment and a first preparation session with the study therapists (see section below for details about the therapy dyads).

Baseline assessment consists in patient-reported questionnaires that patients will complete on paper either on their own prior to V1 or with the help of a study staff member. Baseline assessment includes the following measurements (see details in section 5.1.5): the Functional Assessment of Chronic Illness therapy – Palliative Care (FACIT-Pal); the PROMIS pain interference scale (if pain presented); the Hospital Anxiety and Depression Scale (HADS A and D); the PROMIS social isolation scale; the Life Attitude Profile – revised, Death acceptance subscale (LAP-R, DA); the FACIT-spirituality; the Schedule of Attitudes Toward Hastened Death (SAHD). Consenting caregivers will complete the CarGOQoL and HADS at V1. In addition, the study psychiatrist will complete the C-SSRS and the CAM.

Following baseline assessments, the lead therapist (LT) and the co-therapist (CT) will conduct the first preparation session. The main objectives of the preparation sessions are to educate

patients and families on psilocybin-assisted therapy, to build rapport between them and the study therapists, and to identify intentions for the psilocybin session as well as personal themes and struggles that might impact the psilocybin experience.

V1 and V2 will be conducted within about a week to a month prior to the psilocybin session.

The duration of V1 will be up to 90 min (30 min assessment + 60 min preparation).

Visit V2: preparatory session #2 (patient's home or remote)

The second preparatory session (V2) will take place at home or remotely. Patients and therapists will conduct V2 assessments as indicated on the schedule of assessment (see 5.1.6) and continue to set expectations for treatment, discuss set and setting and build the therapeutic alliance.

The duration of V2 will be up to 75 min (15 min assessment + 60 min preparation).

Visit V3: psilocybin session (hospice facility) – day 0

The psilocybin session will take place in an individual room at the Care Dimensions Hospice House and will last 8 h (30 min assessment + 7h30 hour psychotherapeutic support).

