11. STUDY CALENDAR

11. ST UD		DAK							
	Full screenning + enrollment	Preparation session 1	Preparation session 2	Psilocybin session	Integration session 1 (Day 1)	Integration session 2 (Day 7)	F/U (HOME)	EDC Timepoints	
Visit	VO	V1	V2	V3	V4	V5	V6a,b,,f		
Timing	At least 48h prior to the psilocybin session (V3)	Baseline ≤3 weeks prior to Day 0	≤7 days prior to Day 0	Day 0	Day 1	Week 1 Day 7	Week 3 Monthly after Week 3 Until Week 24 or death	N/A	
Allowable Window					Up to Day 3	Up to Day 14	±14 Day		
Location	Home/Remote	Home/Remote	Home/Remote	Hospice	Home/Remote	Home/Remote	Home/Remote		
Psilocybin				25 mg				V3	
Psychotherapy - min (staff)		60 (LT-CT)	60 (LT-CT)	7h30 (LT-CT)	60 (LT-CT)	60 (LT-CT)		Psychotherapy notes should be captured after V1, V2, V3 V4 and V5	
Assessment - min (staff)	60 (LT-RA)	30 (LT-RA)	15 (LT-RA)	30 (LT-RA)	15 (LT-RA)	30 (LT-RA)	30 (RA)	N/A	
			Clinic	al Assessments and Proced	lures				
Informed consent patient	√							N/A	
Informed consent cargiver	√							N/A	
Demographics	√							V0	
Medical and psychiatric history	√							V0	
Inclusion/exclusion criteria	√							V0	
PPS	√	✓	√	√	√	√	√	During all visits	
САМ	√	✓	√	√	√	√		V0, V1, V2, V3, V4, V5	
C-SSRS (1)	√	✓	√	✓	✓	√		V0, V1, V2, V3, V4, V5	
Vital signs (2)	√			✓				V0, V3	
Physical examination (2)	√			√				V3	
Prior/concomitant medication	√	✓	√	√	√	√		N/A	
Medication taper (if applicable)	√	√	√					NA	
AE/SAEs		✓	√	√	√	√	√	During all visits	
Session recording		✓	√	√	√	✓		NA	
Qualitative interview patient						✓		NA	
Qualitative interview caregiver (3)						√		NA	
Qualitative interview hospice staff							✓	NA	
nospice stan			Particip	pant Completed Assessmen	nts (8)				
DS-II	✓	✓	√	✓	√	√	√	During all visits	
HADS A and D (4)		√	✓	√	√	✓	√	During all visits	
FACIT-Pal 14		✓				√	√	V1, V5, V6a,b,,f	
PIS (6)		✓				√	√	V1, V5, V6a,b,,f	
LAP-R		✓				√	√(7)	V1, V6a	
SIS		√				√	✓	V1, V5, V6a,b,,f	
FACIT-sp		√				✓	✓	V1, V5, V6a,b,,f	
MEQ-30 (5)				✓				V3 or V4	
CEQ (5)				√				V3 or V4	
SAHD		√				✓	√(7)	V1, V6a	
RRPQ						√		V4 or V5	
CarGOQoL (3)		✓				√	√	V1, V5, V6a,b,,f	
Abbreviations IT: Lead Ther		1 1 1 1 1 1 1 1 1 1 1 1 1 1 1 1 1 1 1 1			1	10 : 510/70 !		L	

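### The study-required psychiatric taper can start at V0, before scheduled AE collection, and a registered patient who stops before V1 falls outside the reported AE incidence

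*Combined protocol and SAP*

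**What the plan says.** **The taper is a study requirement.** Section 3.2.9: "Concomitant medications with significant potential to interact with study medications will be exclusionary if they cannot be tapered". The list includes serotoninergic antidepressants, antipsychotics and mood stabilizers. Section 9 names withdrawal effects as the thing the taper should avoid, and gives washouts but no taper lengths.

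**It can begin at V0.** The calendar ticks the taper row at V0, V1 and V2. Registration also follows V0 (5.1.1): "The study staff will follow the registering processes described in Section 4.0".

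**AE collection is scheduled later.** Section 7.4.2 covers "any adverse event (AE) that occurs after initial dose, during treatment, or within 30 days of last treatment". The calendar's AE/SAE row is blank at V0 and ticked from V1. The SAE definition in 7.8 reaches back to screening.

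**V1 timing.** The calendar has "Baseline ≤3 weeks prior to Day 0"; section 5.1.2 has "V1 and V2 will be conducted within about a week to a month prior to the psilocybin session".

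**Patients who do not start.** Sections 4.1 and 4.3: "If the subject does not receive protocol therapy following registration", the subject goes off study, with a date and reason entered.

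**Reporting set.** Section 13.3.2 defines the Safety Population as enrolled participants who receive study treatment. It uses that set for participant accountability and for safety summaries, including AE incidence. The Full Analysis Set is defined instead by receipt of the psilocybin dose.

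**The concern.** Safety is a secondary objective, and the patients are selected for moderate-to-severe demoralization. Withdrawing an antidepressant from such a patient carries its own risk, and the patient takes that risk only in order to join the study. A reader of the AE table will take it to describe the whole regimen, including what a patient must go through to receive it. If withdrawal harm occurs before V1 and the patient leaves, the plan's rules keep that harm out of the AE incidence. Nothing in the plan clearly requires follow-up of the event after the patient goes off study. The pilot is meant to prepare larger trials, so the omission could carry forward.

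**Working it through.** The point rests mainly on reading the rules together. The arithmetic shows only how often the schedule itself forces a taper before V1.

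**1. Follow one registered patient who starts a taper at V0 and stops before V1.**
- Has protocol therapy been given? Section 5.1 describes psilocybin plus two preparation and two integration sessions, and section 5.5 counts therapy the same way. The taper is not part of it, so the answer is no.
- Sections 4.1 and 4.3 then take the patient off study.
- Section 5.6 follows patients removed from protocol therapy for an unacceptable AE until it resolves or stabilizes. It does not clearly reach someone who never began therapy.
- Under 13.3.2 the patient is outside the Safety Population on any reading of study treatment.

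**2. Follow one who attends V1 but is never dosed.** Sections 5.1 and 5.5 suggest preparation counts as treatment, and the contrast with the Full Analysis Set wording points the same way. The term is undefined, so inclusion is open.

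**3. Does the calendar already cover V0?** Its data-capture column says AEs are collected at all visits. The same label is used for the HADS, which is also blank at V0, so the label does not establish V0 collection.

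**4. When must a taper start before the earliest V1?** Days before V1 = max(0, W + T − L).
- W is the listed washout. The table's rule of five half-lives reproduces: fluoxetine 5 × 9 = 45 days; aripiprazole 5 × 75 / 24 = 15.6, listed as 16. Phenelzine is taken as 14 + 7 = 21 under the MAOI rule in section 9.
- T is taper length. The documents give none, so 0, 7 and 14 days are assumed.
- L is the earliest V1: 21 days before dosing (calendar) or 30 (5.1.2, taking a month as 30 days).

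| T (assumed) | L = 21 | L = 30 |
|---|---|---|
| 0 | 1 of 26: fluoxetine 45 − 21 = 24 days | 1 of 26: fluoxetine 45 − 30 = 15 days |
| 7 | 4 of 26: fluoxetine 31, phenelzine 7, aripiprazole 2, diazepam 1 | 1 of 26: fluoxetine 22 |
| 14 | 8 of 26: fluoxetine 38, phenelzine 14, aripiprazole 9, diazepam 8, olanzapine 4, and citalopram, clonazepam and mirtazapine 1 each | 2 of 26: fluoxetine 29, phenelzine 5 |

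Without the five benzodiazepines and zolpidem, which 3.2.9 does not name as a class, the L = 21 counts are 1, 3 and 6 of 20. These are counts of drugs, not patients.

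**5. What the AE table could miss (assumed counts).** Suppose 15 are registered, one has a taper harm and leaves before V1, and 14 are treated. The table shows 0/14 for that harm, with an exact 90% upper limit of 1 − 0.05^(1/14) = 19.3%. Among all registered patients it is 1/15 = 6.7% (0.3% to 27.9%). With two such patients among 15 it is 2/15 = 13.3% (2.4% to 36.3%).

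**The case against.** The best reply is that the protocol already captures these events.

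The opening of section 7 sends all potential AEs to the PI without a dose trigger, to be recorded on a case report form and classified by relationship to the study protocol, a wording that fits a taper harm. Section 7.4.3 makes grade 2 and higher events reportable whatever the attribution, and 7.7 requires all AEs in routine submissions. Section 5.1.5 makes significant suicide risk reportable as an AE or SAE, and the C-SSRS at V1 looks back. Section 9 records medication from screening. Reading preparation as treatment, the start in 7.4.2 coincides with V1, so two of the apparent start points agree. A Safety Population of treated patients is conventional. Dropout reasons are a primary feasibility outcome, and the 60% benchmark counts recruited subjects, so the patient does not vanish from the results. If the 7-day start rule in 4.3 is kept and V1 is the start of intervention, the interval without scheduled contact is at most 7 days.

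Most of this stands. A reader might infer that taper harms would go unrecorded; the documents do not support that, because known events must be reported and graded. What remains is narrower. Retrospective pickup at V1 needs the patient to attend, and no rule puts a recorded pre-V1 event into the AE incidence.

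A reader might also infer that the loss is selective by rule, because section 5.2.1 bars dosing when there is significant suicide risk or delirium. Those criteria apply on the dosing day, to patients already past V1. They do not explain exits before V1.

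**Conclusion.** The point holds as a cheap improvement, not as a flaw in the main analysis. Under the stated rules, a study-required taper can precede scheduled AE collection, and a registered patient who stops before V1 is left out of AE incidence. A patient who attends V1 but is not dosed may be left out; it would be too strong to say that this patient is excluded.

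The number of patients affected is unknown and probably small. The documents do not say how many of the 15 will taper, or for how long. The drug counts depend on assumed taper lengths and should not be read as a patient rate; with no taper time, only fluoxetine forces a pre-V1 start. Whether fluoxetine's 45-day washout fits the 7-day start rule at all is a separate scheduling question, and this point does not depend on it.

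**What to change.** - **7.4.2 and the calendar:** start AE/SAE collection at the first study-driven taper step, or at V1 if there is no taper.
- **4.1 and 4.3:** keep a registered patient who began a taper in AE follow-up until the event resolves or stabilizes, even if never dosed.
- **13.3.2:** add a separate listing of pre-dose AEs for all registered patients, with grade, attribution to the protocol and outcome. Leave the Safety Population table as it is, and say in one sentence whether a preparation session counts as study treatment.

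For a patient tapering before V1, a short AE and suicidality call is already possible under the Unscheduled Visits provision in 5.1.2.

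The cost is amendment wording and perhaps a few calls among 15 patients. The downside is some extra AE entries, many of them due to the underlying disease.

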7.4.3. DF/HCC Adverse Event Reporting Guidelines

Site investigators will report AEs to the sponsor per DF/HCC requirements, and the Dana-Farber Cancer Institute IRB per IRB policies. The table below indicates which events must be reported to the DF/HCC Sponsor Investigator, [name].

DF/HCC Reportable Adverse Events(AEs) to sponsor-investigator						
Attribution	Gr. 2 & 3 AE Expected	Gr. 2 & 3 AE Unexpected	Gr. 4 AE Expected	Gr. 4 AE Unexpected	Gr. 5 AE Expected or Unexpected	
Unrelated Unlikely	5 calendar days	5 calendar days	5 calendar days	5 calendar days*	24 hours*	

Possible Probable Definite	5 calendar days	5 calendar days	5 calendar days	5 calendar days*	24 hours*
----------------------------------	-----------------	-----------------	-----------------	------------------	-----------

^{*} For participants enrolled and actively participating in the study **or** for AEs occurring within 30 days of the last intervention, events must be reported within 1 business day of learning of the event.

7.4.4. Protocol-Specific Adverse Event Reporting Exclusions

For this protocol only, the AEs/grades listed below do not require expedited reporting to the DFCI IRB. However, they still must be reported through the routine reporting mechanism (i.e. case report form).

CTCAE SOC	Adverse Event	Grade	Prolongation of Hospice stay	Attribution	Comments
Gastrointesti nal disorders	Nausea	1,2			The primary effects
	Vomiting	1			of the psilocybin are
	Ataxia	1,2,3		Related	psychological and can bring about a very
	Cognitive	1,2,3			broad range of
	disturbanc				changes in perception
	e				and mood during the
	Depressed	1,2,3			hours the drug is
Nervous system disorders	level of				active. At times,
	consciousn				subjects may
	ess				experience anxiety,
	Dizziness	1,2,3	Up to Day 1		panic, or paranoia.
	Headache	1,2			The majority of reactions from
	Lethargy	1,2			psilocybin change
					rapidly, are easily
	Tremor	1,2,3			managed with proper
	Agitation	1,2,3			guidance and resolve
	Anxiety	1,2,3,4			by the end of the
	Confusion	1,2,3			dosing session (7-10
	Delirium	1,2,3			hours). In many
Psychiatric	Delusions	1,2,3			patients, they may be
disorders					associated with the
	Depression	1,2,3			therapeutic effect of psilocybin-assisted
	Euphoria	1,2,3			therapy.
	Hallucinati	1,2,3			Therefore, such
	ons				expected effects do
	Insomnia	1,2,3			not require expedited

	Psychosis	1,2,3			reporting to the
	Restlessnes s	1,2,3			Principal Investigator or the DFCI IRB as long as they follow the natural arch of the psilocybin effect.
Other AE or SAEs related to underlying terminal condition		1,2,3,4 ,5	GIP	Unrelated	The context of this study – hospice – is defined by the potential for rapid clinical deterioration in enrolled patients. Should such deterioration occur and appear clearly related to the underlying terminal condition in the judgement of the investigators, they do not require expedited reporting to the Principal Investigator or the DFCI IRB

7.5. Reporting to the Food and Drug Administration (FDA)

The Sponsor will be responsible for all communications with the FDA. The Sponsor will report to the FDA, regardless of the site of occurrence, any serious adverse event that meets the FDA's criteria for expedited reporting following the reporting requirements and timelines set by the FDA.

7.6. Reporting to Local Risk Management

Version Date: April 18, 2023

Participating investigators will report to their local Risk Management office any participant safety reports, sentinel events or unanticipated problems that require reporting per institutional policy.

